### 2.2 Study Endpoints/Metrics

#### 2.2.1 Primary Objective Metrics

The quality of fan-beam CT, Truebeam CBCT, and Ethos CBCTs will be compared quantitatively using the following calculated metrics:

- Contrast-to-noise ratio (CNR)
- Resolution
- Hounsfield Unit (HU) accuracy
- Artifact reduction

Furthermore, the three image sets will be evaluated qualitatively by multiple observers with training in radiation oncology and image-guided radiation therapy, who will rank the images acquired for each subject by perceived quality/usefulness for structure contouring and RT guidance.

#### 2.2.2 Secondary Objective Metrics

Dose-volume histograms for key target structures and organs at risk will be calculated from the Ethos and TrueBeam CBCT images and compared to those from the existing dosimetric plan for each patient to determine the accuracy of the dosimetric calculations based on the CBCTs.

The patient experience with CBCT image acquisition will be determined through the use of a questionnaire comparing the TrueBeam CBCT image acquisition process to that of the Ethos CBCT process.

## 3 STUDY DESIGN

### 3.1 Overall Design

This is a single-site feasibility study designed to generate data describing the quality and applicability of on-couch high-performance CBCT imaging technology during external beam radiation therapy.

Subjects who are enrolled in this study will undergo two cone-beam CT image acquisitions in addition to their standard of care. A subject's participation in the study is considered complete once the study CBCTs have been acquired and the questionnaire about the subject's experience of CBCT image acquisition has been completed.

## 4 ELIGIBILITY

### 4.1 Inclusion Criteria

The study will be open to any patient who meets *all of* the following inclusion criteria:

1. Patient age  $\geq 19$
2. Patient is scheduled for treatment on one of the five TrueBeam platforms at the NS Health QE2 site.
3. Patient is receiving radiation therapy using a breath-hold technique (for example, lung, liver and left breast cancers).

### 4.2 Exclusion Criteria

A patient is excluded from the study if they meet *any of* the following criteria:

1. Patient is pregnant or has plans for pregnancy during the period of treatment.
2. Patient is unwilling to consent to participating to the study, or for whom informed consent is not possible.

## 5 Research Plan

### 5.1 Study Methodology

1. The methodology for treatment setup, CT simulation, treatment planning, image guidance and treatment delivery will be determined by the patient's treatment team and is not specified in this protocol. Enrollment in the study may occur after treatment delivery has started but must be prior to the fifth fraction.
2. Following completion of informed consent to participate in this study, the Ethos imaging will be scheduled immediately before or after one of the subject's first five scheduled treatment fractions. While there will be some flexibility in scheduling the session on Ethos, it will be advantageous for the study imaging to be performed as soon as possible after the CT simulation to minimize the potential for anatomical change over time. Two research CBCT images will be acquired, one with breath hold, the other with free breathing.

The Ethos unit will be installed in the same department as the patient's treatment unit therefore the acquisition of the additional study imaging will not require a separate visit. We anticipate the study imaging will require no longer than 15 minutes. No treatment delivery will take place on the Ethos unit during this study.

3. The patient's CT simulation data, TrueBeam CBCT image data and Ethos CBCT data will be exported from the treatment planning system(s) for comparative analysis of image quality as detailed below. The TrueBeam CBCT used in the analysis will be exported from the treatment session delivered on the same day that the Ethos CBCTs are acquired. Data will be anonymized during the export process. Exported image data will be stored in a password-protected folder on the network drive behind hospital firewalls.

### 5.2 Analysis of data

1. Image quality will be quantified by calculating contrast-to-noise ratio (CNR), spatial resolution, Hounsfield Unit accuracy, and presence/absence of artifacts in each of the four image datasets acquired for each subject. This will be done using analysis scripts developed in MATLAB and the Eclipse API (ESAPI, Varian Medical Systems) in the Nova Scotia Health Department of Medical Physics.

CNR will be quantified using

$$\text{CNR} = (|\langle P_{\text{ROI}} \rangle - \langle P_{\text{BG}} \rangle|) / (S_{\text{ROI}}^2 + S_{\text{BG}}^2)^{0.5}$$

where  $\langle P_{\text{ROI}} \rangle$  and  $\langle P_{\text{BG}} \rangle$  are the mean Hounsfield Units (HU) in a selected region of interest and proximal background region, respectively, while  $S_{\text{ROI}}$  and  $S_{\text{BG}}$  are the standard deviations of the HU values in the corresponding regions.

Spatial resolution will be assessed by comparing HU profiles of high-contrast detail in image sets. Artifacts will be assessed qualitatively.

2. The patient's treatment plan, which is originally calculated on the fan-beam CT dataset (as per standard protocol) will be recalculated on both the TrueBeam CBCT and Ethos CBCT datasets using the following process: Target volumes and organ-at-risk contours that are relevant to the anatomy being imaged will be transferred from the original treatment plan onto the CBCTs through an elastic deformation. The accuracy of the contour registration will be verified by a radiation oncologist and contours will be adjusted manually, if necessary, to ensure proper alignment with the underlying image prior to re-calculation of the dose distribution. The dose volume histograms from the original treatment plan will be compared to those generated from the three CBCT-based plans in terms of standard dosimetry metrics, i.e., target volume coverage and organ-at-risk sparing.
3. Anonymized fan-beam CT images, status-quo CBCT image and Ethos CBCT image data sets (with breath hold and with free breathing) will be presented to multiple observers for qualitative assessment of perceived image quality. Observers will include up to five radiation oncologists and five radiation therapists, who will answer questions on image quality for contouring and image guidance purposes, respectively. Image quality will be scored either as a simple ranking (1 to 3) or using a five-point Likert scale. This review will be done using the MeVis framework (see example, Figure 2) that allows centralized user management and authentication, ensuring controlled access to data with unique login credentials for each individual. In the case of Likert scale ranking, analysis will be performed using a Mann-Whitney test.

[figure not shown]

Figure 2 Example of qualitative image review using the MeVis framework.

4. A patient experience questionnaire will be provided to each subject on the day they undergo CBCT imaging on the Ethos platform. Subjects will be encouraged to fill out the questionnaire on that day. Study coordinators will transcribe subject responses into the study database.

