Although IGRT has facilitated breakthroughs in the precision and accuracy of RT over the past two decades, the imaging technology has remained limited in some respects, particularly in the amount of time it takes to acquire a CBCT image. The current acquisition duration of approximately one minute does not allow image guidance in scenarios where high temporal resolution is required. This limitation is most evident in clinical situations where tumours move during treatment delivery, e.g., breast, liver, or lung tumours that move with the patient's respiration. In this scenario, both the CBCT image acquisition and radiation delivery is accomplished at NS Health by the patient performing multiple breath-hold maneuvers in an effort to 'freeze' the motion of the tumour, which may otherwise move by up to 3 cm. Deep Inspiration Breath Hold (DIBH) or Deep Expiration Breath Hold (DEBH) approaches are both used at NS Health, depending on the indication. Because complete acquisition of a CBCT image may require 60 seconds and because many patients who are treated with IGRT have limited ability to maintain DIBH or DEBH for extended periods, up to eight (Boda-Heggemann et al., 2011) separate breath hold maneuvers may be needed to acquire a complete image set.

The multiple-breath-hold CBCT acquisition approach has two key disadvantages. First, the total treatment time is significantly extended, especially if multiple CBCT acquisitions are required (e.g., for pre- and post-alignment of the patient, and particularly for patients with compromised respiratory function, who need time to recover from each breath hold). Longer treatment times impact resources (capital and HR) and are deleterious to the overall patient experience. Second, since each breath hold is not performed identically by the patient (e.g., in terms of breath hold amplitude),

inconsistencies are introduced in the reconstructed image data, resulting in poorer image quality. By forming an image from piecewise sets of projections, one per breath hold, image quality is compromised by motion artifacts (Kashani et al., 2006) due to the variability of the patient's anatomy between projection sets. An example of this from practice, in the context of Stereotactic Ablative Radiation Therapy (SABR) of the liver, is shown in [Figure 1](#).

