## 2 OBJECTIVES AND ENDPOINTS

### 2.1 Study Objectives

The **primary objective** of the study is to compare

- The quality of high-performance Ethos CBCT images (acquired with breath hold and under free breathing) with that of fan-beam CT (CT simulation) acquired with breath hold, where the latter represents a best-case benchmark; and
- The quality of high performance Ethos CBCT images (acquired with breath hold and under free breathing) with that of Truebeam CBCT acquired with breath hold, where the latter represents the status-quo for image guidance.

The **secondary objectives** of the study are:

1. To compare treatment dosimetry calculated on the Ethos CBCT images to that calculated on both the fan-beam CT and the Truebeam CBCT.
2. To compare the patient experience of CBCT image acquisition between the Ethos CBCT and the existing Truebeam CBCT.

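### The DVH comparison with the original breath-hold plan mixes CBCT dose error with real anatomical differences, so it should not be read as dose accuracy, least of all for the free-breathing Ethos scan

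*Combined protocol and SAP*

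**What the plan says.** Section 2.1 describes the reference image as "fan-beam CT (CT simulation) acquired with breath hold, where the latter represents a best-case benchmark". Section 5.1, item 2 sets out the study imaging: "Two research CBCT images will be acquired, one with breath hold, the other with free breathing". It takes place at one of the first five fractions. Imaging soon after simulation is encouraged "to minimize the potential for anatomical change over time", but no maximum interval is set. Under item 3 of the same section, the TrueBeam CBCT comes from the treatment session on the same day.

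Section 5.2, item 2 recalculates the plan on the CBCTs. Contours are carried over by elastic deformation and checked by a radiation oncologist; "contours will be adjusted manually, if necessary, to ensure proper alignment with the underlying image prior to re-calculation of the dose distribution". Then: "The dose volume histograms from the original treatment plan will be compared to those generated from the three CBCT-based plans". Section 2.2.2 gives the purpose: "to determine the accuracy of the dosimetric calculations based on the CBCTs". Section 10.1 summarises the dosimetry by means and standard deviations of DVH metrics. It gives no test, tolerance or separate treatment by breathing state.

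For image quality, Section 5.2, item 1 calculates HU accuracy in all four image sets, fan-beam CT included, without naming a reference value.

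**The concern.** A DVH recalculated on a CBCT can differ from the original for two kinds of reason: the CBCT's HU values or artifacts lead to a wrong dose, or the patient's anatomy really was different when that scan was taken. Only the first is a matter of accuracy.

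The plan assigns the whole difference to accuracy. Yet the protocol's own case for breath hold is that anatomy differs without it: Section 1.1 describes tumours "which may otherwise move by up to 3 cm". A free-breathing CBCT with perfect HU values could therefore give a different DVH from the breath-hold plan and be reported as dosimetrically inaccurate. A breath-hold CBCT could likewise be marked down because the patient had changed since simulation.

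At stake is the secondary objective on dosimetry, which Section 1.1 links to whether the CBCT images are suitable for dosimetric planning. Free-breathing imaging is also the mode that Section 1.1 hopes will help patients who cannot hold their breath, so a misattributed result there would matter.

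**Working it through.** There is no stated figure to reproduce: Section 10.1 gives 30 subjects, with at least 7 in each of three cohorts, but no alpha, power, effect size, SD or margin. The check is therefore a decomposition of each contrast, followed by an illustration.

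**Inputs from the documents.** Reference: plan on breath-hold fan-beam CT (2.1, 5.2). Recalculated sets: TrueBeam breath hold, Ethos breath hold, Ethos free breathing (2.1, 5.1, 5.2). The three CBCTs share a day (5.1, item 3).

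**Notation.** For any DVH metric, let e be the dose error due to the CBCT itself, with e_T for TrueBeam, e_B for Ethos breath hold and e_F for Ethos free breathing. Let s be the shift from breath hold to free breathing, and d the shift from anatomical change between simulation and the imaging day.

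- Ethos free breathing minus plan = e_F + s + d
- Ethos breath hold minus plan = e_B + d
- TrueBeam breath hold minus plan = e_T + d
- Ethos breath hold minus same-day TrueBeam breath hold = e_B − e_T, apart from breath-hold variation within the day
- Ethos free breathing minus same-session Ethos breath hold = (e_F − e_B) + s

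Only the e terms are accuracy. Editing contours on each CBCT limits contour-transfer error. It leaves s and d in place, because the DVH then describes the anatomy on that scan.

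**Illustration.** Assume no CBCT error at all (every e = 0), n = 30, and shifts s and d in units of the SD of the paired difference. The values of s and d are assumptions, and the fourth contrast is given exact cancellation. The plan specifies no test; a two-sided 5% paired t-test is used only to show how often a difference would stand out (20,000 simulated studies per row).

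| s | d | Free breathing vs plan: mean shift, % non-zero | Ethos breath hold vs plan: mean shift, % non-zero | Ethos vs TrueBeam breath hold, % non-zero |
|---|---|---|---|---|
| 0 | 0 | 0, 5% | 0, 5% | 5% |
| 0.5 | 0 | 0.5, 76% | 0, 5% | 5% |
| 0.5 | 0.25 | 0.75, 98% | 0.25, 26% | 5% |
| 1 | 0.5 | 1.5, 100% | 0.5, 75% | 5% |

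**Effect of sample size.** The 95% confidence half-width for a paired mean is t(0.975, n−1)/√n SDs. This is 0.37 SD at n = 30 and 0.93 SD at n = 7. More subjects narrow the interval, but around e + s + d rather than e.

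**The case against.** The strongest reply is that the protocol already handles much of this. It takes the TrueBeam CBCT on the same day, makes Ethos versus TrueBeam dosimetry an explicit objective, encourages early imaging and has an oncologist check the contours. It is also a feasibility study reporting means and SDs without a pass or fail rule. Nothing says the three CBCT-based plans will be pooled.

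Much of that stands. The same-day breath-hold contrast largely cancels s and d, so a reader who inferred that every planned dosimetric comparison is confounded would go too far. But that contrast shows which device is closer to the other, not whether either is accurate, and Sections 2.2.2 and 5.2 define accuracy against the original plan. Free-breathing Ethos against breath-hold TrueBeam still contains s. Early imaging is encouraged rather than required, and does nothing about s. A descriptive result is misread just as easily as a tested one.

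Two stronger readings are tempting and are not supported:

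- A reader might set the 3 cm motion figure against a typical planning margin and conclude that target coverage must fail on the free-breathing scan. The figure is a maximum for motion without breath hold, not the usual offset between breathing states. The documents give no margin. The Synopsis speaks of registered image sets, and nothing states how the beams are positioned on each CBCT, so a full uncorrected offset cannot be assumed.
- A reader might infer that HU accuracy is stated to be judged against the planning CT. The benchmark wording in 2.1 suggests it, but 5.2 calculates HU accuracy for the fan-beam CT as well, and no section names the reference. What can be said is that the reference is undefined.

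**Conclusion.** The point holds for the contrasts with the original plan. As written, the free-breathing DVH difference mixes CBCT dose error with breathing state and change since simulation; the breath-hold differences mix it with change since simulation. Calling either one accuracy is not justified by the design, and the free-breathing result is the more exposed. The same-day Ethos and TrueBeam breath-hold contrast is largely unaffected, subject to breath-hold variation within the day.

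The size cannot be derived from the documents. The percentages above depend on assumed shifts and show only that moderate anatomical differences could be visible at n = 30 with no imaging error. The conclusion itself needs only that s or d is not zero, which the protocol's own background and scheduling advice take for granted. The sample size is not affected. On HU, the gap is a missing definition.

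**What to change.** In Sections 2.2.2 and 5.2, item 2:

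1. Base dose-accuracy conclusions on the Ethos and TrueBeam breath-hold CBCTs only. State that their differences from the original plan include anatomical change since simulation, and report the interval from simulation to CBCT.
2. Name same-day Ethos breath hold versus TrueBeam breath hold as the main dosimetric device comparison, and describe it as relative error.
3. Report the free-breathing Ethos DVH separately as a descriptive contrast that includes breathing-state effects, for example against the same-session Ethos breath-hold scan. Do not label it accuracy.
4. Optionally, add as a sensitivity reference a planning CT warped to each breath-hold CBCT, with dose recalculated on it, provided that the image-level deformation is itself checked. The existing oncologist check covers contour registration only, and where contours had to be edited the warped image may not match them.

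In Section 5.2, item 1, name the HU reference. If it is the fan-beam CT, do not score that CT against itself, and do not read free-breathing lung HU differences as HU error.

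Items 1 to 3 and the HU definition need wording and tabulation from data already collected, with no new imaging or patient burden. Item 4 would add up to 2 dose calculations per subject (2 × 30 = 60), plus the work of warping and checking the images.

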### 5.3 Informed consent

All participating patients will be required to give written informed consent, indicated by a dated signature of the subject or legal representative. The process for obtaining informed consent shall comply with the ISO 14155:2020 and applicable national regulations and shall use language that is understandable by the patient. The original signed consent form shall be retained on file and a copy shall be given to the patient.

## 6 ADVERSE EVENTS

### 6.1 Expected Adverse Events

There are no adverse events expected from participation in this study. However, any adverse events attributed to participation in the study (“definitely”, “probably”, or “possibly” related) by the Principal Investigator will be documented and entered in the study database. Adverse events will be classified per CTCAE version 5.0. No other adverse events, including those that are attributed to the subject’s cancer treatment, will be recorded in the study database.

### 6.2 Adverse Event Definitions

Adverse events are “any unfavorable and unintended sign (including an abnormal laboratory finding), symptom, or disease temporally associated with the use of a medical treatment or procedure that may or may not be considered related to the medical treatment or procedure.”

A Serious Adverse Event (SAE) is any untoward medical occurrence, unintended disease or injury, or untoward clinical signs (including abnormal laboratory findings) in participants, users, or other persons, whether or not related to the investigational medical device\* that:

- Led to a death,
- Led to serious deterioration in the health of the participant, that either resulted in
  - a life-threatening illness or injury, or
  - a permanent impairment of a body structure or a body function, or
  - in-patient or prolonged hospitalization\*\*, or
  - medical or surgical intervention to prevent life-threatening illness or injury or permanent impairment to a body structure or a body function
- Led to fetal distress, fetal death or a congenital abnormality or birth defect.

**\*NOTES:**

- NOTE 1 This definition includes events related to the investigational medical device or the comparator.
- NOTE 2 This definition includes events related to the procedures involved.
- NOTE 3 For users or other persons, this definition is restricted to events related to investigational medical devices.

**\*\*NOTE** Planned hospitalization for a pre-existing condition, or a procedure required by the CIP, without serious deterioration in health, is not considered a serious adverse event.

Hospitalization means admitted to hospital for at least 24 hours. An emergency room, urgent care, or infusion center visit is not a hospitalization.

## **6.3 Adverse Event Reporting**

Study staff are required to notify the Principal Investigator of any serious adverse event (SAE). SAEs must be reported to the REB according to REB reporting requirements. The Principal Investigator must report SAEs to the study sponsor within 72 hours of becoming aware of the event.

Sponsor contact for AE reporting:

[name]  
[contact]  
Email: [contact]

## **7 DEVICE ISSUES**

Any problems with the Ethos platform (including any device failures or malfunctions) will be documented and reported to the sponsor.

Per ISO 14155:2020, the following definition applies:

- Device Deficiency: inadequacy of a medical device with respect to its identity, quality, durability, reliability, safety or performance  
NOTE Device deficiencies include malfunctions, use errors, and inadequate labeling.

## **8 PROTOCOL DEVIATIONS**

Protocol deviations and other problems with study execution will be documented and reported to the sponsor and to the REB per REB reporting requirements.

## 9 DATA COLLECTION

### 9.1 Confidentiality Procedures

Only data that are required for the endpoints of the study will be collected. Study data include basic demographic information (age, sex), the location of the patient's tumor, co-morbidities that would affect breathing, and information about the image acquisitions. No data that can directly identify the subjects will be entered into the study database. Subjects will be represented in the study database by unique study identifiers. The relationship between patients and their study identifiers will be maintained in a protected master list located in a protected folder within the NSHA firewall (separate from the study database) to which only NS Health study personnel will have access.

All data that could directly identify the subject will be removed from the images collected for this study when they are exported from the clinical systems on which they are acquired.

